#### **9.7 Cellular Analysis**

The number of IFN- $\gamma$  and IL-5 producing T-cells (CD4+ and CD8+) from PBMCs responsive to vaccine antigens will be listed and summarized by time point using appropriate descriptive statistics for each part by treatment.

Additional details for cellular analysis are presented in the SAP.

#### **9.8 Safety Analysis**

Safety Population will be used for all safety variables specified.

All safety data will be summarized by part and treatment. No statistical tests will be performed.

Subjects who are seropositive and seronegative at screening will also be summarized and safety and efficacy subgroup analysis will be performed for these groups of subjects.

Additional details for safety analysis are presented in the SAP.

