### **3.2.2 Secondary Endpoints**

Safety:

- Unsolicited AEs, MAAEs, and AESIs up to Day 43
- SAEs, MAAEs, NOCDs, and AESIs up to Day 365 (approximately 1 year after first vaccination)

Immunogenicity:

- Vaccine ELISA of both RBD IgG and IgM antibodies and neutralizing antibody titers for each treatment group:
  - GMT at baseline and Days 15, 22, 43, 90, 181, 273, and 365
  - GMT ratio ( $GMT_{placebo}/GMT_{TAP-COVID-19}$ ) at baseline and Days 22, 29, 43, 90, 181, 273, and 365
  - GMFR at Days 8, 22, 29, 43, 90, 181, 273, and 365 relative to baseline
  - Seroconversion rates on Days 8, 15, 22, 29, 43, 90, 181, 273, and 365. Seroconversion is defined as the proportion of subjects at the respective time point that have detectable antibodies (IgG and IgM) against SARS-CoV-2 Spike Protein RBD following challenge with vaccine (and potentially by natural asymptomatic or symptomatic infection by the virus in case of a placebo subject).
  - GMI on Days 8, 22, 29, 43, 90, 181, 273, and 365

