### **9.3 Randomization**

The overall randomization for the study will be 2:1 (active:placebo). Each Part (A and B) and treatment (low and high) will be randomized individually 2:1 (active to placebo).

The study will start with Part A (18-49 years) low dose, randomized in a 2:1 ratio (30 subjects active:15 subjects placebo) for Treatment A (15 µg TAP-COVID-19 vaccine + 0.5 mg CpG).

Part A (18-49 years) high dose will be randomized in a 2:1 ratio (30 subjects active:15 subjects placebo) for Treatment B (45 µg TAP-COVID-19 vaccine + 0.5 mg CpG) after Part A low dose has completed enrollment and the iSRC has reviewed safety and tolerability data through Day 8.

Part B (50-85 years) low dose will be randomized in a 2:1 ratio (30 subjects active:15 subjects placebo) for Treatment A (15 µg TAP-COVID-19 vaccine + 0.5 mg CpG) after Part A low dose has completed enrollment and received the first vaccination and the iSRC has reviewed safety data through Day 8.

Part B (50-85 years) high dose will be randomized in a 2:1 ratio (30 subjects active:15 subjects placebo) for Treatment B (45 µg TAP-COVID-19 vaccine + 0.5 mg CpG) after Part B low dose has completed enrollment and received the first vaccination and the iSRC has reviewed safety data through Day 8.

A total of 90 subjects will be randomized in Part A (18-49 years); 30 subjects low dose (Treatment A, 15 µg TAP-COVID-19 vaccine + 0.5 mg CpG), 30 subjects high dose (Treatment B, 45 µg TAP-COVID-19 vaccine + 0.5 mg CpG), and 30 subjects placebo (Treatment C).

A total of 90 subjects will be randomized in Part B (50-85 years); 30 subjects low dose (Treatment A, 15 µg TAP-COVID-19 vaccine + 0.5 mg CpG), 30 subjects high dose (Treatment B, 45 µg TAP-COVID-19 vaccine + 0.5 mg CpG), and 30 subjects placebo (Treatment C).

Treatment A: TAP-COVID-19 vaccine (15 µg) + CpG (0.5 mg) IM injection on Day 1 and Day 22 ( $\pm 3$  days)

CONFIDENTIAL

Treatment B: TAP-COVID-19 vaccine (45 µg) + CpG (0.5 mg) IM injection on Day 1 and Day 22 ( $\pm 3$  days)

Treatment C: Placebo (buffered saline solution) IM injection on Day 1 and Day 22 ( $\pm 3$  days)

A computer-generated randomization schedule for each part (Part A, Part B, and Part C Expansion) will be generated prior to study start by an ICON biostatistician.

For sentinel dosing, 3 subjects from each part will be randomized 2:1 (active:placebo). The remainder of each cohort will also be randomized 2:1 (active:placebo).

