#### **9.5 Interim Analyses**

An unblinded interim analysis will be performed on the safety and immunogenicity data collected for each of the 4 dose groups (Part A low dose, Part A high dose, Part B low dose, and Part B high dose). Unblinded interim analysis will occur for the Part A low dose group (including active and placebo subjects) when the first 30 subjects vaccinated have data available from Day 1 through Day 43. The remaining cohorts will have an unblinded interim analysis performed when all subjects in the cohort have data from Day 1 through Day 43. For the interim analysis, treatment codes will be unblinded after the data are deemed ready for the analysis and the data has been monitored. The CRO [except for the unblinded team members preparing the data for unblinded iSRC review], Investigator, and clinical staff will not have access to the unblinded treatment group interim analyses and will remain blinded until completion of the study. The Sponsor will be unblinded at the interim analysis. Safety and immunogenicity analyses from this unblinded interim analysis will be presented in a CSR. This CSR may be submitted to regulatory authorities as needed.

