#### **9.6 Immunogenicity Analysis**

The mITT Population will be used for all listings and summary statistics corresponding to immunogenicity analysis.

The individual sampling and blood collection for ELISA analysis to determine IgG and IgM antibody titers to the spike RBD and neutralizing antibody titers for parent (Wuhan) and any variant SARS-CoV-2 strains, will be listed and summarized by time points for each part by treatment.

All derived immunogenicity secondary endpoint parameters: GMT, GMT ratio, GMFR, GMI, and seroconversion rates will be listed and summarized by scheduled time point using descriptive statistics (n, mean, SD, minimum, median, maximum, geometric mean, CV%, GeoCV%, and 95% CI) for each part by treatment.

PBMC and serum sample data for future research results at each scheduled visit will also be provided separately in a listing and summary table, if applicable.

Subgroup analysis for safety and efficacy will be performed for those subjects who were seropositive when enrolled.

Graphical display of the summary results or at individual time points will be provided as needed (eg, scatter plots of subject titer values to visually display individual data points).

Additional details for analysis of immunogenicity are presented in the SAP.

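### Sections 9.6 and 9.8 pool placebo across two separately randomised, sequential dose cohorts; placebo should also be shown by cohort, and high versus low labelled non-randomised and non-concurrent

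*Combined protocol and SAP*

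**What the plan says.** Section 9.3 states "Each Part (A and B) and treatment (low and high) will be randomized individually 2:1 (active to placebo"), with 30 active and 15 placebo subjects per cohort. Part A high dose is randomised "after Part A low dose has completed enrollment and the iSRC has reviewed safety and tolerability data through Day 8", and Part B follows the same order. The same section then adds up each Part as 30 low dose, 30 high dose "and 30 subjects placebo (Treatment C"), that is, placebo as one treatment.

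The analysis sections follow that last count. Section 9.8: "All safety data will be summarized by part and treatment". Section 9.6: titres "will be listed and summarized by time points for each part by treatment", and the derived parameters, including the GMT ratio, are "summarized by scheduled time point using descriptive statistics (n, mean, SD, minimum, median, maximum, geometric mean, CV%, GeoCV%, and 95% CI"), again for each part by treatment. Neither section names a cohort column, a cohort term or a covariate. Both leave further detail to a separate SAP.

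Section 3.1.2 lists high versus placebo, low versus placebo and high versus low as adverse event comparisons: unsolicited events through Day 43, and serious, medically attended, new-onset chronic and special-interest events through Day 365. Section 3.2.2 sets the GMT ratio "at baseline and Days 22, 29, 43, 90, 181, 273, and 365".

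Section 9.5 is laid out differently. The Day 1–43 interim is run for each of the four dose groups, the first "for the Part A low dose group (including active and placebo subjects").

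**The concern.** Randomisation protects the comparison of each dose with the 15 placebo subjects of its own cohort. It does not protect the comparison with the other cohort's 15, who enrolled in a different period, and no subject is ever randomised between high and low dose.

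The background could differ between periods. Seropositive subjects may enrol if PCR-negative (4.1), a positive SARS-CoV-2 test is reported as an adverse event of special interest (8.2.2), and follow-up to Day 365 covers later calendar time for the later cohort. With pooled placebo, such a shift enters the low-dose and high-dose contrasts with opposite signs. It can therefore look like a dose gradient, and high versus low takes the whole shift.

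**Working it through.** **Plan's own figures.** No power calculation exists to reproduce (9.1). The allocation reproduces: 30 + 15 = 45 per cohort; 2 × 45 = 90 per Part, as 30:30:30; 4 × 45 = 180.

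**Bias.** Let the background mean be μ in the low-dose cohort and μ + D in the high-dose cohort, with pL and pH placebo subjects. The pooled placebo mean is μ + wD, where w = pH/(pL + pH).
- Low − pooled placebo: error −wD.
- High − pooled placebo: error +(1 − w)D.
- High − low: error D.

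At 15 + 15, w = 0.50, giving −D/2, +D/2 and D. If the high-dose cohort had stopped at 16:8 (an assumption), w = 8/23 = 0.35, giving −0.35D and +0.65D.

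**Cost of splitting, in SD units.**
- Pooled: √(1/30 + 1/30) = 0.258.
- Own cohort: √(1/30 + 1/15) = 0.316, a ratio of 1.22.
- High versus low through each cohort's placebo: √(2 × 0.100) = 0.447, or 1.73 times the direct contrast.
- At 16:8, high dose: √(1/16 + 1/23) = 0.326 against √(1/16 + 1/8) = 0.433, a ratio of 1.33.

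**Break-even drift.** Pooling has the lower mean squared error until (D/2)² exceeds 0.1000 − 0.0667 = 0.0333, so D = 0.37 SD. Multiplying by √(p(1 − p)) gives 8, 11 and 15 percentage points at event rates of 5%, 10% and 20%.

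**Coverage of the 95% CI for the dose–placebo GMT ratio.** With b = D/2 and SE 0.258, coverage is Φ(1.96 − b/SE) − Φ(−1.96 − b/SE): 93%, 89% and 84% at D = 0.2, 0.37 and 0.5 SD.

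**Serostatus example (all values assumed).** Seropositivity is 10% in the low-dose cohort and 20% in the high-dose cohort. Mean log10 titres for naive/seropositive subjects are 0.7/2.0 on placebo and 1.6/2.6 vaccinated, SD 0.4. The background shift is D = 1.3 × 0.10 = 0.13 log10. As dose over placebo (the protocol's ratio is the inverse):
- Full size: 10^(−0.065) = ×0.86 for low dose and 10^(+0.065) = ×1.16 for high dose.
- 16:8: 10^(−0.13 × 0.348) = ×0.90 and 10^(+0.13 × 0.652) = ×1.22.

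In this example placebo titres do not change from baseline, so placebo fold rise is 1 whatever the serostatus mix, and a GMFR contrast avoids the error even with pooled placebo. Simulation (4,000 runs, baseline noise SD 0 or 0.4) agrees: the GMFR contrast and an ANCOVA with treatment, cohort and baseline titre are both within about ×1.01.

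**Chance imbalance.** At 10% seropositivity, one SD of the log10 ratio is √(0.09 × (1.0²/n_active + 1.3²/n_placebo)). This gives ×1.23 for 30 v 30, ×1.30 for 30 v 15 and ×1.44 for 16 v 8. Raw own-cohort GMT ratios should therefore not stand alone.

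**Rare events.** With zero events, the 95% upper limit 1 − 0.025^(1/n) is 11.6% for n = 30 and 21.8% for n = 15. This is a reason to keep the pooled column.

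**The case against.** The case for leaving the plan alone is substantial.

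- **Baseline serostatus is already visible.** The GMT ratio is reported at baseline, GMFR is a secondary endpoint with a 95% CI, and serostatus subsets are planned (9, 9.6, 9.8). In the example above, GMFR removes the error. This stands, and it makes the adjusted GMT ratio supplementary. However, the plan gives GMFR per group rather than as a dose–placebo contrast. With pooled placebo, GMFR also does not absorb a difference between periods in infection after baseline. None of these displays sets an adverse event rate against a dose's own controls.
- **Days 1–43 are organised by dose group (9.5) and reported in a CSR.** The final analysis covers Day 43 to Day 365 (9). This also stands: unsolicited events and early titres are the lesser part of the concern. Section 9.5 does not specify table layouts, and 9.6 and 9.8 do not repeat its structure for later data.
- **The SAP may already show cohorts.** It may. Its text was not available, so the point concerns the protocol wording only.
- **The study is descriptive and splitting loses precision.** Both are true. Named comparisons and confidence intervals are nevertheless planned, and the pooled column would stay.
- **Section 9.3 already discloses the sequence.** It does, but 3.1.2 lists high versus low beside the two placebo comparisons without a distinction.

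**Conclusion.** The point holds at modest size. As written, 9.6 and 9.8 do not give each dose a comparison with its own randomised placebo for adverse events through Day 365. They do not adjust the all-subjects GMT ratio for cohort or baseline, and high versus low is not marked as non-randomised and non-concurrent. The bias is −D/2, +D/2 and D at full size. D, the titres, the seropositivity and the 16:8 cohort are assumptions. At D = 0.2 SD the CI still covers 93%; by 0.5 SD coverage falls to 84%.

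A reader might infer more than the documents support:
- *That drift occurred.* No passage gives a drift or a seropositivity rate.
- *That the high-dose cohorts ended short.* Amendment 8 records that enrolment ceased, but gives no cohort sizes.
- *That the primary endpoint is compromised.* Solicited reactions within 7 days of each dose fall in the Day 1–43 period organised by dose group, and no shift in them is indicated.
- *That pooled placebo is wrong and should go.* Below about 0.37 SD of drift it has the lower mean squared error.

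**What to change.** In 9.6 and 9.8, or in the SAP if it does not already do so:

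1. Keep the pooled placebo column and show placebo by cohort beside it, with the actual n in each, so that the own-cohort layout of 9.5 carries through to Day 365.
2. As a supplementary analysis for all subjects in each Part, report the dose–placebo GMT ratio with 95% CI at each post-baseline visit from an ANCOVA of log10 titre on treatment, cohort and baseline log10 titre. Place it beside the unadjusted ratio and read it with GMFR. It is estimation only, so it fits the no-testing policy.
3. Label high versus low as non-randomised and non-concurrent, with each cohort's placebo rate beside it.

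The cost is wording and programming; no new data are needed. Own-cohort contrasts have about 22% larger standard errors at 30:15 (33% for high dose at an assumed 16:8). In the simulation with equal seropositivity of 10% or 20% in both cohorts, the ANCOVA standard error was roughly 0.8 to 1.1 times the pooled unadjusted one at full size. It can cost precision when baseline titre is noisy or few subjects are seropositive. Neither display should replace the other.

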## **10 ACCESS TO SOURCE DATA/DOCUMENTS**

The Investigator will provide direct access to source data and documents for individuals conducting study-related monitoring, audits, IRB review, and regulatory review. The Investigator must inform the study subject that his/her study-related records may be reviewed by the above individuals without violating the subject's privacy of personal health information in compliance with HIPAA regulations.

Attention is drawn to the regulations promulgated by the FDA under the Freedom of Information Act providing, in part, that information furnished to clinical Investigators and IRBs will be kept confidential by the FDA only if maintained in confidence by the clinical Investigator and IRB. By signing this protocol, the Investigator affirms to the Sponsor that the Investigator will maintain, in confidence, information furnished to him or her by the Sponsor and will divulge such information to the IRB under an appropriate understanding of confidentiality with such board.

CONFIDENTIAL

## **11      QUALITY CONTROL AND QUALITY ASSURANCE**

Sponsor/ICON will implement and maintain quality control and quality assurance procedures with written SOPs to ensure the study is conducted and data are generated, documented, and reported in compliance with the protocol, GCP, and applicable regulatory requirements.

### **11.1      Conduct of Study**

This study will be conducted in accordance with the provisions of the Declaration of Helsinki and all revisions thereof (Tokyo 2004), and in accordance with FDA CFR (§312.50 and §312.56) and the ICH E6 Guidelines on GCP (CPMP/ICH/135/95). Specifically, this study is based on adequately performed laboratory and animal experimentation; the study will be conducted under a protocol reviewed by an IRB; the study will be conducted by scientifically and medically qualified persons; the benefits of the study are in proportion to the risks; the rights and welfare of the subjects will be respected; the physicians conducting the study do not find the hazards to outweigh the potential benefits; and each subject will give his or her written, informed consent before any protocol-driven tests or evaluations are performed.

The Investigator may not deviate from the protocol without a formal protocol amendment having been established and approved by an appropriate IRB, except when necessary to eliminate immediate hazards to the subject or when the change(s) involve only logistical or administrative aspects of the study and are approved by the Sponsor. Any deviation may result in the subject having to be withdrawn from the study, and may render that subject nonevaluable.

#### **11.1.1      Protocol Deviations**

A protocol deviation is defined as any intentional or unintentional change to, or noncompliance with, the approved protocol procedures or requirements. Deviations may result from the action or inaction of the subject, Investigator, or site staff.

At the outset of the study, a process for defining and handling protocol deviations will be established. This will include determining which violations will be designated “key,” requiring immediate notification to the medical monitor and/or Sponsor. The Investigator is responsible for seeing that any known protocol deviations are recorded and handled as agreed.

#### **11.2      Protocol Amendments**

Only the Sponsor may modify the protocol. Amendments to the protocol will be made only after consultation and agreement between the Sponsor and the Investigator. All amendments that have an impact on subject risk or the study objectives, or require revision of the ICF, must receive approval from the IRB prior to their implementation.

#### **11.3      Monitoring of Study**

The Investigator will permit the CRA to review study data as frequently as is deemed necessary to ensure data are being recorded in an adequate manner and protocol adherence is satisfactory.

The Investigator will provide access to medical records for the monitor to verify eCRF entries. The Investigator is expected to cooperate with the Sponsor or a designee in ensuring the study adheres to GCP requirements.

The Investigator may not recruit subjects into the study until the Sponsor or a designee has conducted a site initiation visit (in-person or via teleconference) to review the protocol and eCRF in detail.

## **12 ETHICS**

### **12.1 Institutional Review Board Approval**

#### **12.1.1 Ethics Review Prior to Study**

The Investigator will ensure that the protocol and ICF are reviewed and approved by the appropriate IRB prior to the start of any study procedures. The IRB will be appropriately constituted and will perform its functions in accordance with FDA regulations, ICH GCP guidelines, and local requirements as applicable.

#### **12.1.2 Ethics Review of Other Documents**

The IRB will approve all protocol amendments (except for Sponsor-approved logistical or administrative changes), written informed consent documents and document updates, subject recruitment procedures, written information to be provided to the subjects, available safety information, information about payment and compensation available to subjects, the Investigator's curriculum vitae and/or other evidence of qualifications, and any other documents requested by the IRB and regulatory authority as applicable.

### **12.2 Written Informed Consent**

The nature and purpose of the study will be fully explained to each subject. The subjects must be given ample time and opportunity to inquire about details of the study, to have questions answered to their satisfaction, and to decide whether to participate. Written informed consent must be obtained from each subject prior to any study procedures being performed.

## **13 DATA HANDLING AND RECORD KEEPING**

### **13.1 Data Reporting and Case Report Forms**

#### **13.1.1 Case Report Forms**

The Investigator will be provided with eCRFs, and will ensure all data from subject visits are promptly entered into the eCRFs in accordance with the specific instructions given. The Investigator must sign the eCRFs to verify the integrity of the data recorded.

#### **13.1.2 Laboratory Data**

A list of the normal ranges for all laboratory tests to be undertaken forms part of the documentation to be collated prior to study start. If a central laboratory has been selected to conduct any or all tests, it is essential all samples be analyzed at that laboratory. The Investigator must maintain source documents such as laboratory reports and complete history and physical examination reports.

#### **13.1.3 Retention of Source Documents**

The Investigator must maintain source documents such as laboratory reports, x-rays, ECGs, consultation reports, and complete history and physical examination reports.

### **13.2 Retention of Essential Documents**

The study essential documents must be maintained as specified in the ICH guidelines for GCP and the applicable regulatory requirements. The Investigator/institution should take measures to prevent accidental or premature destruction of these documents.

Essential documents should be retained until at least 2 years after the last approval of a marketing application in an ICH region and until there are no pending or contemplated marketing applications in an ICH region or until at least 2 years have elapsed since the formal discontinuation of clinical development of the study vaccine. These documents should be retained for a longer period; however, if required by the applicable regulatory requirements or by an agreement with the Sponsor. It is the responsibility of the Sponsor to inform the Investigator/institution as to when these documents no longer need to be retained.

## **14 ADMINISTRATIVE INFORMATION**

### **14.1 Financing and Insurance**

Financing and insurance will be addressed in a separate agreement between the Sponsor and the Investigator.

### **14.2 Publication Policy**

The Sponsor will retain ownership of all data. All proposed publications based on this study will be subject to Sponsor's approval requirements.

**APPENDIX A DIARY CARD EXAMPLE**

Example Diary Card may be adjusted to add additional subject collection information or CRU and/or subject contact information.

